## **4. BACKGROUND**

### **4.1 Early Stage Non-small cell Lung Cancer (NSCLC)**

Lung cancer is the number one cause of cancer related mortality in men and women in the US. The majority of patients present after they become symptomatic and are diagnosed with advanced stage disease. However, approximately 10-15% of patients present with early stage I NSCLC. Treatment is critical in these patients as Stage I-II NSCLC left untreated results in a median OS of 1 year and median 5-year OS of 10%. The primary treatment modalities for early stage lung cancer include surgical resection or definitive stereotactic body radiation therapy alone. Nevertheless, even with current standard of care SBRT in patients with early stage NSCLC the 3 year overall survival has been reported at 36-52% due to a high rate of distant metastatic disease. Thus, additional systemic therapies are critically needed in this population to decrease relapse rates and improve overall survival.

Surgical resection is indicated in patients with early stage NSCLC who are medically operable with good performance status. Definitive SBRT alone is the preferred treatment option for medically inoperable patients or those who refuse surgery. SBRT is also an appropriate option for patients with high surgical risk (able to tolerate sublobar resection but not lobectomy [eg, age  $\geq 75$  years], poor lung function). Definitive SBRT for early stage lung cancer has an excellent local control rate of greater than 90% which compares favorably with surgery[2]. However, the distant relapse free survival rate with surgery or SBRT for early Stage I NSCLC is approximately 80%, and hence approximately one out of every five patients will develop recurrent disease. Given this high failure rate there is a critical need to improve regional and distant control in the patient population. Checkpoint blockade immunotherapy targeting PD-1/PD-L1 has known activity in NSCLC and thus represents an ideal class of systemic agents to test in this patient population.

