### **4.3 Stereotactic Body Radiation Therapy (SBRT)**

Radiation therapy has a long and established history in the field of oncology[12]. Recently, technological advances have allowed radiation oncologists to effectively treat tumors anywhere in the body using SBRT[13]. This ability to deliver high tumoricidal doses while limiting dose to surrounding normal structures has been a major advance and fundamental shift in the field of radiation oncology. The term stereotactic radiation or stereotaxy refers to the use of a referenced three-dimensional coordinate system to locate targets inside the body and deliver highly focused beams of radiation to that site with millimeter accuracy. Stereotactic delivery of radiation is usually termed stereotactic body radiation therapy (SBRT) for extracranial tumors, and referred to as Stereotactic Radiosurgery (SRS) for intracranial tumors. Because of the accuracy and ability to precisely modify the radiation dose distribution to minimize radiation to normal tissue, stereotactic radiation allows for "hypofractionation" or delivery of very high doses of radiation during each fraction of treatment. In the United States, clinical stereotactic radiation courses are currently completed in 1 to 5 fractions total. This is a dramatic shortening of total treatment time compared to conventionally fractionated radiation which can range from between 2-8 weeks or 10-40 fractions to complete. Clinically, stereotactic radiation achieves excellent local

control rates in early stage NSCLC.

Specifically, RTOG 0236 (Timmerman R, JAMA. 2010) was a Phase II Study evaluating 55 patients with peripheral T1-T2N0 NSCLC[2]. The patients received SBRT 18Gy x3 fractions over 1.5-2 weeks. With a median followup of 2.9 years the authors reported a 3 year local control of 98%, 3 year loco-regional control of 87% and 3 year Distant Metastasis rate of 22% with a median OS of 48 months. The authors reported 13% Grade 3 toxicity, 4% Grade 4 toxicity, and no Grade 5 toxicity and concluded that definitive SBRT for patients with inoperable NSCLC results in high rates of local tumor control.

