### **11.5.3 Clinical Response Parameters**

**Time to Local Progression (TTLP)** is defined as the elapsed time from the start of treatment to the date of documented local progression or death, whichever happens earliest.

**Relapse-Free Survival (RFS)** is defined as the time from starting treatment to the time of first documented tumor progression or death due to any cause, whichever occurs first. Death is considered as an event here. For subjects whose disease does not progress or who do not die, PFS will be censored at the time of the last visit.

**Time to Progression (TTP)** is defined as the time from starting treatment to the time of first documented tumor progression. Subjects who do not progress will be censored at the time of the last contact. In addition, death from any cause will also be censored.

**Overall Survival (OS)** is defined as the time from starting treatment until death due to any cause. For subjects who do not die, time to death will be censored at the time of last contact.

**Locoregional Control (LRC)** is defined as the time from starting treatment until local and/or regional relapse is documented

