#### **15.2 Sample Size/Accrual Rate**

Phase I: The purpose of the Phase I part of this study is to evaluate the tolerability and safety profile SBRT combined with concurrent and adjuvant Avelumab at 10mg/kg. For this purpose, 12 subjects will be enrolled. Although the sample sizes are not based on statistical power considerations, data from these subjects will provide toxicity and dosing information on administration Avelumab in combination with SBRT in patients with early Stage NSCLC. The accrual rate is estimated at 3 patients per month.

Phase II: The primary endpoint will be relapse free survival (RFS) rate at median followup of 2 years. The accrual rate is estimated at 3 patients per month, and the patients will be

followed for up to 3 years. A total of 56 patients will be entered in the study accounting for a 10% dropout rate. This study would have 80% power to detect a 10% absolute improvement in RFS at 2 years from 80% to 90% using a one-sided t-test at significance level 0.10. RFS estimate at 2 years was based upon analysis of relevant literature[55-57].

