### 15.4 Analysis of Primary Objectives

Phase I: If no more than one-third of the subjects permanently discontinue study medication prior to completing six doses due to treatment related adverse events then this combination will be deemed as tolerable and return to the IRB, DMC, and Sponsor for further evaluation and approval prior to proceeding to the Phase II cohort.

If  $\geq 4$  patients in the Phase I cohort permanently discontinue study medication prior to completing six doses due to treatment related adverse events then we will suspend the study and return the study to the IRB and DSMB committees for further evaluation and recommendations.

Phase II: The primary efficacy analysis will be the relapse free survival (RFS) rate in patients with early Stage NSCLC receiving SBRT combined with concurrent and adjuvant Avelumab compared to SBRT alone historical controls. The analysis population includes all registered subjects who have received SBRT and at least 2 cycles of Avelumab.

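### The 80% SBRT-alone null for 2-year RFS is not reconciled with an endpoint that counts every death, and it sits above what the survival quoted in the protocol would suggest

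*Combined protocol and SAP*

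**What the plan says.** Section 15.2 sets the Phase II design: "This study would have 80% power to detect a 10% absolute improvement in RFS at 2 years from 80% to 90" per cent, with a one-sided t-test at level 0.10 and 56 patients entered, said to allow for 10% dropout. The only support for the 80% is one sentence: "RFS estimate at 2 years was based upon analysis of relevant literature[55-57". It does not say which endpoint, time point, population or figure was taken from each reference. By title, references 55 and 56 concern operable patients and reference 57 inoperable patients.

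Section 15.4 describes the primary analysis as RFS in patients "receiving SBRT combined with concurrent and adjuvant Avelumab compared to SBRT alone historical controls", and gives no control figure of its own. It adds: "The analysis population includes all registered subjects who have received SBRT and at least 2 cycles of Avelumab".

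Section 11.5.3 says that RFS "is defined as the time from starting treatment to the time of first documented tumor progression or death due to any cause", and states separately that death counts as an event.

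On SBRT alone, section 4.1 says "the 3 year overall survival has been reported at 36-52" per cent. Section 4.3 describes a 55-patient phase II trial "with a median OS of 48 months", and a 70-patient phase II trial in medically inoperable patients with 3-year OS of 43% and cancer-specific survival of 82%. The only 80% in the background is in section 4.1: an approximate distant relapse free survival rate after surgery or SBRT, with no time point, read there as one patient in five recurring.

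Section 5.1 limits enrolment to patients who are medically inoperable or decline surgery.

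**The concern.** In a single-arm trial the null rate does the work of the control group, and 80% is the only number the plan offers for it. An 80% rate is easy to accept for freedom from relapse. It is much harder to accept for an endpoint that also counts deaths from other causes, in patients of whom many are unfit for surgery. The 70-patient series shows how far apart the two kinds of measure can be: 82% cancer-specific survival against 43% OS at the same three years.

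If the death-inclusive SBRT-alone rate in the enrolled patients is below 80%, a true 10-point gain no longer reaches 90%. The trial could then read an active regimen as a failure.

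**Working it through.** **Inputs.** Null 0.80, alternative 0.90, one-sided alpha 0.10, 56 entered, 10% dropout (section 15.2). RFS definition (section 11.5.3). Three-year OS 36-52% (section 4.1), 43% with n = 70, and median OS 48 months (section 4.3). Assumed: 50 evaluable (56 × 0.9 = 50.4) and 2-year status known for all of them.

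**1. The plan's own figure.** With the arcsine approximation, power = Φ(2[asin√0.9 − asin√0.8]√n − 1.2816). This gives 0.800 at n = 56 and 0.766 at n = 50, so 56 fits 80% power as the evaluable number.

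The plan states no cut-off, but its t-test implies one. With 50 patients, t = (p̂ − 0.80)/√(p̂(1 − p̂)/49), against a critical value of 1.299:
- 43 of 50: t = 0.06/0.0496 = 1.21, not significant.
- 44 of 50: t = 0.08/0.0464 = 1.72, significant.

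Success therefore means at least 44 event-free. The exact binomial probability is 0.103 at a true 80% and 0.770 at a true 90%. The fair benchmark below is 77%.

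**2. A check without a survival model.** Suppose 2-year OS were 80%. At most 20% die in the first two years. The share of 2-year survivors who must then die in year 3 is 1 − OS(3)/0.80:
- to reach 52%: 1 − 0.52/0.80 = 0.35
- to reach 43%: 1 − 0.43/0.80 = 0.46
- to reach 36%: 1 − 0.36/0.80 = 0.55

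**3. Implied 2-year OS, the ceiling on RFS.** For Weibull shape k, OS(2) = OS(3)^((2/3)^k), or 0.5^((24/48)^k) from the median. Shape 1 is constant hazard.

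| Quoted figure | k = 1 | k = 1.5 | k = 2 | k needed for 80% |
|---|---|---|---|---|
| 3-year OS 36% | 0.506 | 0.573 | 0.635 | 3.75 |
| 3-year OS 43% | 0.570 | 0.632 | 0.687 | 3.28 |
| 3-year OS 52% | 0.647 | 0.701 | 0.748 | 2.65 |
| Median 48 months | 0.707 | 0.783 | 0.841 | 1.64 |

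Sampling error does not close the gap in the 70-patient series. SE = √(0.43 × 0.57/70) = 0.059, so the upper 95% limit is 0.546. That gives 0.668 at k = 1 and 0.764 at k = 2. RFS is lower than each of these figures once non-fatal relapse is counted.

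**4. Consequence of a lower control rate.** Probability of at least 44 of 50 event-free, for a true 10-point gain and, alternatively, for the planned hazard ratio ln 0.9/ln 0.8 = 0.472:

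| True SBRT-alone RFS | +10 points | Hazard ratio 0.472 |
|---|---|---|
| 80% | 0.770 | 0.770 |
| 78% | 0.607 | 0.685 |
| 75% | 0.361 | 0.546 |
| 70.7% | 0.127 | 0.354 |

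**5. Direction.** If the control rate is 75% and Avelumab adds nothing, the chance of success is 0.019, against 0.103 at 80%. The error is conservative.

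**6. Power if the null is moved.** Exact test, n = 50, one-sided 0.10, +10 points:

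| Null | Cut-off | Power |
|---|---|---|
| 60% | 35 | 0.569 |
| 65% | 38 | 0.511 |
| 70% | 40 | 0.584 |
| 75% | 42 | 0.668 |

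On the same exact basis the present 80% null needs 45 of 50 and has power 0.616.

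**The case against.** The plan says that the 80% came from references 55-57, which cannot be seen here and may report a 2-year rate that counts all deaths. The enrolled patients may also do better than the quoted series. Those who decline surgery are eligible, so operable series are relevant to part of the mix. Sections 5.1 and 5.2 require a life expectancy of at least 9 months, ECOG status of 2 or better, adequate oxygen saturation and renal function, and no significant active cardiac disease. The analysis population also requires at least 2 Avelumab cycles, which removes the earliest failures.

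The quoted survival is not uniform either. A 48-month median implies a 3-year OS of at least 50%, or 0.5^(36/48) = 59% under constant hazard, which is above the range in section 4.1. That series allows 80% OS at two years if the hazard rises moderately.

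Most of this stands, and it rules out two stronger readings. A reader might infer that 80% is wrong, or that the distant relapse figure in section 4.1 was carried into section 15.2 by mistake. The documents support neither: no 2-year OS is quoted, the references are unseen, and the match of the two numbers is no proof of origin.

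The objection does not supply the missing argument, because the protocol nowhere says why its patients should outlive the series it cites. The 48-month median is weak support: it lies beyond the follow-up of that trial ("With a median followup of 2.9 years the authors reported"), and RFS would still be lower than OS. How far eligibility raises the control rate cannot be calculated from the documents.

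**Conclusion.** The concern holds as an unreconciled and doubtful benchmark. Under constant hazard the quoted survival caps 2-year SBRT-alone RFS at about 51-71%. The three 3-year figures stay at or below about 75% even at Weibull shape 2. Only the 48-month-median series reaches 80% OS, at shape 1.64 or more.

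The loss depends on the unknown true control rate. Against a benchmark of 77%, a real 10-point gain succeeds about 61% of the time from 78%, 36% from 75% and 13% from 70.7%. Near 80% the loss is modest, and at a constant hazard ratio it is smaller throughout. These figures assume 50 evaluable patients with complete 2-year status and the cut-off of 44.

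A reader might also infer that the null inflates false claims of benefit. It does not: a null set too high makes such claims rarer. Because testing against a mismatched null could give the wrong answer, this is more than a gap in referencing. The plan should be changed, though confidence that 80% is too high is only moderate.

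**What to change.** In section 15.2, set one deciding null equal to a 2-year SBRT-alone RFS that counts death from any cause and matches the enrolled mix of inoperable and surgery-refusing patients. State the endpoint definition, time point, population and figure taken from each source. Listing what references 55-57 report is not enough by itself if endpoint or population differs.

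If the resulting figure is not 80%, replace 80%/90% in section 15.2, align the hypothesis in section 1, and restate the power at the planned size (step 6 gives about 57%, 51%, 58% and 67% for nulls of 60%, 65%, 70% and 75%).

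In section 15.4, name that single null as the comparator and report 2-year RFS with its one-sided 90% lower bound against it. Any other null should be labelled a descriptive sensitivity analysis that cannot support a claim of benefit. The safeguard matters: if the true rate is 70% with and without Avelumab, a 60% null (at least 35 of 50) would be cleared about 57% of the time.

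Cost: an amendment to sections 1, 15.2 and 15.4, and extraction of figures from sources the documents do not reproduce. The stated power becomes less favourable than 80%. Keeping 80% power for a 10-point gain would take more patients, by n = ((1.2816√(p0(1 − p0)) + 0.8416√(p1(1 − p1)))/0.10)²: about 103 evaluable at a 60% null and 74 at 75%. That increase is not requested.

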### 15.3 Safety Run-In Phase

There is no significant published experience with SBRT used concurrently with Avelumab in this study population. Therefore, to ensure that the combination is safe, the first six patients will be treated and observed for toxicity for 30 days after radiation before continuing with further treatment. 6 patients will be enrolled at the proposed dose of Avelumab and SBRT. If  $\leq 3$  patients among the safety cohort have a defined toxicity event within 30 days of therapy, we proceed with additional accrual with this regimen to complete a total of 12 patients. If  $\geq 4$  patients among the safety cohort have defined toxicity events we will suspend the study and have the study reviewed by IRB and DSMB committees for further recommendations.

*Toxicity Event:*  $\geq$  grade 3 adverse event (CTCAE v 4.0) with an attribution of possible, probable, or definite.

### 15.4 Analysis of Primary Objectives

Phase I: If no more than one-third of the subjects permanently discontinue study medication prior to completing six doses due to treatment related adverse events then this combination will be deemed as tolerable and return to the IRB, DMC, and Sponsor for further evaluation and approval prior to proceeding to the Phase II cohort.

If  $\geq 4$  patients in the Phase I cohort permanently discontinue study medication prior to completing six doses due to treatment related adverse events then we will suspend the study and return the study to the IRB and DSMB committees for further evaluation and recommendations.

Phase II: The primary efficacy analysis will be the relapse free survival (RFS) rate in patients with early Stage NSCLC receiving SBRT combined with concurrent and adjuvant Avelumab compared to SBRT alone historical controls. The analysis population includes all registered subjects who have received SBRT and at least 2 cycles of Avelumab.

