#### 12.4 Stereotactic Body Radiation Treatment

It is reasonable to extrapolate expected toxicity rates from the current experience and reported literature with SBRT. One significant toxicity is radiation pneumonitis, which can be manifested as fever, increased exertional dyspnea, pleuritic chest pain, and peritumoral infiltrate on chest imaging. It generally occurs between 1 to 3 months of completion of radiotherapy. The risk of grade 2-4 radiation pneumonitis is approximately 10-20% in patients treated with conventional large field radiotherapy and higher in patients treated with combined chemoradiotherapy. It is highly dependent on the volume of the lung treated to high dose and the mean lung dose.

Importantly SBRT has a significantly better tolerated with a limited side effect profile compared to conventional large field radiation. For example the rates of Radiation

Pneumonitis with SBRT have been reported as less than 5%. At this point, the incidence of RT pneumonitis from SBRT combined with immunotherapy for small pulmonary tumors is unknown. However, if the proposed radiation dose constraints are used the risk should be <10% with the proposed dose level.

Other toxicities commonly associated with such treatment includes colitis, diarrhea, hypophysitis, rash, arthritis, fatigue, nausea, vomiting, anorexia, and weight loss. Some of these symptoms could also be due to tumor progression. Clinical and radiographic assessments will be performed as indicated to identify all adverse effects, ascertain their etiology, and provide the most appropriate palliative measures. Complications will be graded according to the Common Toxicity Criteria, National Cancer Institute, version 4.0.

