## **15. STATISTICAL CONSIDERATIONS**

### **15.1 Endpoints**

#### **15.1.1 Primary Objectives**

Phase I: The Phase I primary endpoint is safety and tolerability as described in Section 3.1.1. Tolerability and safety of will be determined after all patients have completed six doses or have discontinued dosing prior to completing six doses. Safety analyses will be performed in all treated subjects. Descriptive statistics of safety will be presented using National Cancer Institute (NCI) Common Terminology Criteria for Adverse Events (CTCAE) version 4.0.

Phase II: The Phase II primary endpoint is to determine the relapse free survival rate at a median followup of 2 years in early stage NSCLC treated with definitive SBRT combined with 6 cycles of concurrent and adjuvant Avelumab.

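### Sections 15.1.1 and 15.4 set no minimum follow-up after SBRT for the Phase I tolerability decision, so at its earliest it can fall inside the protocol's own 1–3 month pneumonitis window for 3–4 of 12 patients

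*Combined protocol and SAP*

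**What the plan says.** Section 15.1.1 has Phase I tolerability and safety "determined after all patients have completed six doses or have discontinued dosing prior to completing six doses". Section 15.4 gives the criterion: "If no more than one-third of the subjects permanently discontinue study medication prior to completing six doses due to treatment related adverse events", the combination is deemed tolerable and must then "return to the IRB, DMC, and Sponsor for further evaluation and approval prior to proceeding to the Phase II cohort". Neither section, nor the monitoring plan in Section 13, names a minimum time since SBRT.

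Section 12.4 says of radiation pneumonitis: "It generally occurs between 1 to 3 months of completion of radiotherapy". It adds that "the incidence of RT pneumonitis from SBRT combined with immunotherapy for small pulmonary tumors is unknown". The same section reports rates below 5% with SBRT alone and expects a risk below 10% if the proposed dose constraints are used.

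Section 15.3 adds a run-in for the first six patients only. One sentence says "the first six patients will be treated and observed for toxicity for 30 days after radiation before continuing with further treatment". The rule for proceeding then counts patients who "have a defined toxicity event within 30 days of therapy". The suspension sentence ("patients among the safety cohort have defined toxicity events we will suspend the study") repeats no window. Section 15.3 does not define therapy. Section 6.5 uses the word for the whole course of about 3 months.

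**The concern.** The decision point is tied to dosing, while the toxicity of most interest is timed from the end of radiation. If six doses finish before the stated onset window closes, the regimen can be labelled tolerable and sent for Phase II approval while the most recently enrolled patients are still at risk of an event whose rate the protocol calls unknown.

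The rule cannot pick up such an event later either. Once dose six has been given, nothing remains to discontinue, so a later pneumonitis cannot count under Section 15.4. It reaches the decision-makers only through the safety summaries, SAE reports and DMC review, and none of these is tied to 3-month post-SBRT data.

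**Working it through.** **Inputs.** Six doses, 14 days apart, each on day 1 of its cycle (6.3.1). First SBRT fraction 3–10 days after starting cycle 1 (6.3.2). Four or five fractions, every other day (6.5). Onset window 1–3 months after radiotherapy (12.4), taken here as days 30–90. Twelve patients at 3 per month (15.2), taken as one every 10 days. Days are counted from dose one as day 0.

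**The plan's own figure.** 6 × 14 = 84 days, or 2.76 months, which agrees with the approximately 3 months in Section 6.5.

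**Time since SBRT at dose six.**
- Fractions every other day span (4 − 1) × 2 = 6 to (5 − 1) × 2 = 8 days.
- SBRT ends between day 3 + 6 = 9 and day 10 + 8 = 18.
- Dose six on time is day 5 × 14 = 70.
- Time since SBRT: 70 − 18 = 52 to 70 − 9 = 61 days.
- Left until day 90: 90 − 61 = 29 to 90 − 52 = 38 days.

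**Patients still in the window.** The cohort's total window is 12 × 60 = 720 patient-days. Each earlier patient is 10 days further on than the next.

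| Decision for patient 12 | SBRT ended day 9: days since SBRT, latest patients | SBRT ended day 18: days since SBRT, latest patients | Patients under 90 days | Unobserved patient-days |
|---|---|---|---|---|
| Day 70 (dose six, on time) | 61, 71, 81, 91 | 52, 62, 72, 82 | 3–4 | 29+19+9 = 57 to 38+28+18+8 = 92, i.e. 8–13% |
| Day 84 (end of cycle 6, or one slipped cycle) | 75, 85, 95 | 66, 76, 86, 96 | 2–3 | 15+5 = 20 to 24+14+4 = 42, i.e. 3–6% |
| Day 100 (30 days after dose six) | 91 | 82, 92 | 0–1 | 0 to 8, i.e. 0–1% |

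**Sensitivity.** Taking three months as 91.3 days and allowing weekday-only fractions raises the upper end to 5 patients in the first row and 2 in the last. With random (Poisson) accrual at the same rate, the first-row count has a median of 4 (5th to 95th percentile 2 to 8). The 3–4 patients in the first row are all among the last six enrolled, so the pause after the run-in does not change the count.

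**Scale in expected cases.** The documents give no onset distribution. Assume that all onsets fall in days 30–90, evenly spread. At a 10% risk, 12 × 0.10 × (8–13%) gives about 0.10–0.15 cases not yet seen at the earliest decision. At 5% it is about 0.05–0.08.

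**The window in Section 15.3.** Counted from the end of radiation, it closes at day 30, just as the onset window opens. Counted from the end of the full course, it closes at day 70 + 30 = 100 or day 84 + 30 = 114, which is 82–91 or 96–105 days after SBRT. The two wordings can therefore differ by 52–75 days.

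**The case against.** The strongest reply is that little goes unobserved and nothing is lost. The figure of 3–4 patients assumes a decision on the very day of the last sixth dose, and time spent on review shortens the gap. At least 8 of 12 patients have then completed the window. Even the last patient is 52–61 days past SBRT, beyond the 1-month and 6-week assessments in the study calendar. All treated patients enter the safety summaries (15.1.1, 15.6). SAEs are reported through 90 days after treatment, which is day 70 + 90 = 160, or 142–151 days after SBRT, unless new anti-cancer therapy starts (12.5.2). The DMC sees all available data and may meet ad hoc (13). All of this stands and keeps the point small. It does not remove it: the reviewers may ask for 3-month data, but the plan does not make those data a condition of the decision.

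Four stronger readings are tempting, and the documents do not support them.

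- **Late pneumonitis would be missed, or the tolerable label alone opens Phase II.** The reporting provisions above and the approval step in Section 15.4 rule out both.
- **About half the risk escapes the rule.** With on-time dosing, 29–38 of the 60 window days (48–63%) do fall after dose six. That is calendar time, not a share of cases, and a later cut-off would not change it, because Section 15.4 is a dose-completion criterion.
- **The suspension sentence in Section 15.3 counts events at any time.** It is the second branch of one rule, so the window naturally carries over from the first.
- **Section 15.3 pauses each run-in patient's own dosing.** This fits poorly with dosing every 2 weeks. The next sentences speak of additional accrual, which is the more natural meaning.

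**Conclusion.** The point holds as a minor gap in a stated decision point. Sections 15.1.1 and 15.4 allow the Phase I determination before the onset window in Section 12.4 has closed for every patient. At the earliest decision this affects 3–4 of 12 patients and 8–13% of the cohort's window time, falling to about 1 patient (0–2) if the 30-day post-treatment visit is awaited. These figures assume on-time dosing except where stated, even accrual at the planned rate, and a window of days 30–90. Under the protocol's own risk expectation, the expected number of unseen cases is well below one. The case for acting rests on the low cost and on the stated uncertainty about the combination, not on a large expected loss.

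The two wordings of the observation window in Section 15.3 are a separate inconsistency and need reconciling whatever view is taken of the timing.

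**What to change.** In Sections 15.1.1 and 15.4, set the data cut-off for the pre-Phase II safety review at the 3-month post-SBRT visit of the last Phase I patient. As part of the approval already required, give the IRB, DMC and Sponsor a table of toxicity events, as defined in Section 15.3, in all 12 patients through that visit. The table is needed because a later cut-off alone would not bring events after dose six into the discontinuation rule. What number is acceptable is for the investigators and the DMC to set.

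In Section 15.3, reconcile the two statements of the observation window, use the agreed wording in both branches of the rule, and say what further treatment refers to.

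The cost is amendment wording and one table. No visit is added, since the calendar already has AE evaluation at 3 months after SBRT. The cut-off falls on day 9 + 90 = 99 to 18 + 90 = 108 for the last patient. That is 29–38 days after an on-time sixth dose, about 4–5 weeks (25–42 days with the calendar's ±4 days). If the last patient slipped one cycle, it is 99 − 84 = 15 to 108 − 84 = 24 days after dose six.
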